### 3. DESCRIPTION OF DESIGN AND TRIAL POPULATION

#### 3.1 OVERALL TRIAL DESIGN AND PLAN

This multicentre, multinational, randomised, double-blind, parallel group, comparator-controlled study compares treatment with linagliptin (5 mg once daily) to treatment with glimepiride (1-4 mg) as monotherapy or as add-on therapy to metformin and/or other antidiabetic treatment as specified in Section [3.3.2](#).

The trial is event driven and will run with an estimated number of 6000 patients for an estimated treatment time of 432 weeks, beginning with the randomisation of the first patient. In the case the number of events is not or may not be reached within this period the trial duration and/or the number of patients enrolled will be increased until the defined number of adjudicated primary events is reached.

Patients will enter an open-label placebo (add-on) run-in period of 2 up to 4 weeks before randomisation. Patients who successfully complete at least two weeks of the placebo-run (should have a treatment compliance between 80% to 120%) and who still meet the inclusion/exclusion criteria will be randomised to receive either linagliptin or glimepiride. Patients who do not successfully complete at least two weeks of the placebo run-in, may continue the placebo run-in phase up to four weeks to meet the compliance criterion as specified above. Any SU or glinide will be discontinued at randomisation Visit 2 (SU/glinide should not be taken in the morning of Visit 2).

The randomised treatment will be double-blind within the dose groups of linagliptin and glimepiride (i.e. each patient will receive one active treatment and placebo matching the alternative active treatment in a double-dummy design).

[figure not shown]

Figure 3.1: 1 Treatment periods and treatment groups in the trial design

For all patients, contacts are scheduled at regular time intervals ([see flow chart](#)). The estimated treatment duration for the first randomised patient is 432 weeks. The End of Treatment Visit (EOT) activities will be performed when a patient discontinues study medication permanently. Patients who discontinue study drug prematurely should be observed until study end as if they were still receiving blinded study treatment, but no (safety) laboratory sampling (including pregnancy test), ECG or vital signs will be required. If a patient who prematurely discontinued study drug is not willing to return

at the pre-defined regular visit schedule at minimum a yearly telephone call and a telephone call at study end will be asked for (through the patient or alternative person designated by the patient), to document the occurrence of outcome events and vital status. If possible, also other AE's and concomitant therapy changes since last visit should be recorded.

All patients will have a follow up visit 30 days following completion of the treatment period. The follow-up visit may be performed as a phone visit for patients who completed the planned treatment period and who do not have any abnormalities at the EOT visit (only adverse events/outcome events and changes in concomitant therapy to be obtained).

The number of confirmed adjudicated primary endpoint events will be continuously monitored during the trial. Based on the available number of events the projected number of expected future events will be calculated. As soon as the projection reliably suggests that the total number of patients with a by adjudication confirmed primary endpoint event will reach 631, the trial team will perform respective actions to stop the trial. From this time point on, all patients are expected to perform their last visit (EOT visit) within the proposed time schedule, communicated via an investigator letter. A follow-up visit will take place 30 days after the EOT visit.

In case early study termination is to be performed (e.g. based on recommendation by the DMC), a reasonable timeframe to stop the trial (perform last patient visits) will be defined and communicated to the investigators.

### **3.1.1 Administrative structure of the trial**

The study is sponsored by Boehringer Ingelheim. The following committees will participate in the conduct of the trial, their specific functions are summarised below:

#### Steering Committee

A Steering Committee (SC) will have a scientific and clinical advisory function in the study. The Steering Committee is composed by university and sponsor based scientists with clinical and methodological expertise.

#### Data Monitoring Committee

An independent Data Monitoring Committee (DMC) will review safety and efficacy data and make recommendations whether to continue the study, continue the study with modifications, or terminate the study. The DMC analyses and operations will be formally separated from the sponsor, the investigators and the steering committee.

#### Clinical Event Committees

The study is set up with prospective adjudication of all cardio/cerebrovascular pancreatic trigger events. The prospectively defined adjudication process will assess cardiac and neurological vascular events through an independent, blinded, external Clinical Event Committee (CEC). Details on the composition of the committee, its

**Proprietary confidential information.**

© 2019 Boehringer Ingelheim International GmbH or one or more of its affiliated companies. All rights reserved.

This document may not - in full or in part - be passed on, reproduced, published or otherwise used without prior written permission.

procedures and interactions are provided in a separate CEC Charter. Additionally, a separate independent, blinded, external committee will be set up for adjudication of pancreatic events. The adjudication process for these events will be clarified in a separate CEC charter.

### 3.2 DISCUSSION OF TRIAL DESIGN, INCLUDING THE CHOICE OF CONTROL GROUP

According to current guidelines of the ADA/EASD, metformin should be initiated concurrently with lifestyle intervention at diagnosis in patients newly diagnosed with T2DM when HbA1c > 7.0% and be titrated to a maximum tolerated dose (up to 2x 1000 mg/day or total 2500 mg/day) [R09-1164]. Therefore, patients enrolling on metformin monotherapy represent an important proportion of patients with T2DM. However, contraindications or intolerance to metformin due to e.g. congestive heart failure or severe renal impairment also constitutes a significant amount of people with T2DM. Further, local guidelines may indicate other first line treatment. Therefore this trial also allows for patients that are treatment naïve or are on other antidiabetic treatments as specified in Section [3.3.2](#).

Treatment with linagliptin is compared against glimepiride, a drug from the second most widely used antidiabetic class after metformin (i.e. SUs). Treatment goal for HbA1c is in this trial, according to most international guidelines, ≤ 7.0%. During the trial additional therapy (“rescue therapy”) is allowed, and encouraged, if HbA1c > 7.5% during maintenance phase. This is considered important as to ensure that an optimal level of standard of care is reached. However, the decision to initiate rescue medication remains with the investigator and the appropriate local treatment guidelines.

The protocol also encourages the investigators to treat all other CV risk factors (lipid levels, blood pressure, micro/macroalbuminuria, unhealthy lifestyle, smoking) according to an optimal level of standard of care. In a high CV risk population this usually implies liberal use (if tolerated or not contraindicated) of statins, ACE-inhibitors, AT-II receptor blockers, aspirin, beta-blockers, calcium channel blockers, etc.). This should be conducted in the context of local or regional guidance for primary or secondary CV prevention.

The treatment period is planned for up to an estimated 432 weeks. The treatment period will be followed by a follow-up period of 30 days.

### 3.3 SELECTION OF TRIAL POPULATION

Approximately 10000 patients will be screened for the trial in about 45 countries. Approximately 700 trial centres will be participating to randomise the estimated number of 6000 patients.

Participating sites are expected to randomise a least 8 patients. Investigators who fail to randomise at least one study subject in the first 12 weeks of the trial may be excluded from further participation. If enrolment is delayed, additional centres may be recruited.

Screening of patients for this trial is competitive, i.e. screening for the trial will stop at all centres when a sufficient number of patients has been randomised to trial treatment. Investigators will be notified when the appropriate number of patients has been screened and screening is complete, and will not be allowed to recruit additional patients for this study. Patients who have completed Visit 1a procedures prior to notification of the termination of recruitment will be allowed to continue in the study, if they meet all entry criteria.

The check for subject eligibility will be based upon a complete medical history including a physical examination and clinical laboratory tests. Judgement of the clinical relevance of a concomitant disease is at the discretion of the investigator. Conditions under therapy are always clinically relevant.

A log of all patients included into the study (i.e. having given informed consent) will be maintained in the ISF at the investigational site irrespective of whether they have been treated with investigational drug or not.

Re-screening and/or re-testing (of assessments) is permitted under certain circumstances. Whilst the information provided below is not an exhaustive list, it provides some guidance as to when such re-screening and/or re-testing would be considered appropriate. If a site is in any doubt as to whether re-screening and/or re-testing is appropriate in their particular situation, then clarification should be sought with the CML.

#### Re-testing:

Re-testing is only to be performed for a lab result which is obviously received beyond stability at the central laboratory or thought to be a spurious result. It is not permitted to perform re-testing (in any time window after V1a sampling) for HbA1c when it does not meet the study criteria only.

#### Re-screening:

- Re-screening of the same patient is only allowed once.
- The patient should be declared a screening failure in the eCRF/RDC with their original patient number.
- Upon re-screening, the next available (= new) patient number should be selected from RDC.
- The patient must be re-consented using the current approved version of the information sheet and consent form.
- There is no time limit for re-screening – as long as the patient fits the eligibility criteria they could be re-screened whenever the investigator feels they may become eligible.

### 3.3.1 Main diagnosis for study entry

Patients with documented diagnosis of T2DM with insufficient glycaemic control and at high risk of CV events prior to informed consent can be enrolled in the study. Any antidiabetic background medication at Visit 1a should be on a stable (unchanged) daily dose for at least 8 weeks. There is no short term use of insulin within 8 weeks prior informed consent. Background medication should be stable during screening/run-in phase to allow randomisation.

As local guidelines for management of T2DM will be followed, treatment naïve T2DM patients should be offered first line anti-diabetic treatment (e.g. metformin) before allowing them for study inclusion, unless they have specific contra-indications or intolerances to its use (see also [Section 2.1](#)).

Prior SU or glinide treatment will be discontinued at Visit 2, whereas if medications such as metformin and alpha-glucosidase inhibitor are being used, these should be continued.

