#### 4.1.4 Drug assignment and administration of doses for each patient

Following the screening period and the placebo run-in period, patients who qualify will be randomised (Visit 2) to one of the dosage and treatment schedules outlined in [Table 4.1.4: 1](#) below. Medication will be dispensed in a double-blind and double-dummy manner as either 5 mg linagliptin (plus glimepiride placebo) or an initial dose of 1 mg /day of glimepiride (plus linagliptin placebo). IXRS will allocate medication kit numbers at each scheduled in-clinic visit (V2 – 31). At visits 2-5 patients will receive one treatment box, sufficient for 4 weeks treatment (plus 1 week reserve). At visits 6- 31 patients will receive one treatment box, sufficient for 16 weeks (plus two weeks reserve) of treatment.

After the starting dose of 1 mg/day, glimepiride/ glimepiride placebo has to be uptitrated in 4 week intervals during the first 16 weeks of treatment to the next dose to a potential maximum dose of 4 mg/day, if the fasted HBGM values are > 110 mg/dl (6.1 mmol/l) at the day of visit 3, 4 and 5 (in-clinic HBGM measurement at the day of the visit), unless the investigator considers that it would place the patient at an increased risk for hypoglycaemia. The average HBGM value of previous recent fasting HBGM measurements prior to the day of visit (from the patient's HBGM diary) could also be used to guide uptitration at the discretion of the investigator, if there is a meaningful discrepancy between the single fasted HBGM value at the day of the visit in the clinic and this average HBGM value.

Patients on previous glimepiride may continue on their previous glimepiride dose up to Visit 2 (SU/glinide should not be taken in the morning of Visit 2). These patients will start the glimepiride/glimepiride placebo at their pre-trial glimepiride dose. If prior glimepiride dose was  $\geq 4$  mg/day, the patient will start the glimepiride/glimepiride placebo in the randomisation phase at a dose of 4 mg/day combined with 5 mg/day linagliptin/ linagliptin placebo. Patients on a previous SU, that is not glimepiride, or glinide should start glimepiride /glimepiride placebo at Visit 2 at a starting dose of 1 mg/day combined with 5 mg/day linagliptin/ linagliptin placebo.

The patients will be instructed to bring their HBGM devices to a visit for an additional measurement of fasted glucose during the titration phase, and if required, during maintenance phase ([see flow chart](#)).

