### 7.3.2 Secondary analyses

All other secondary analyses are of exploratory nature, no correction for multiple hypotheses testing will be made. All statistical tests and confidence intervals are two-sided with a significance level of  $\alpha=0.05$  and will include the factor treatment, unless stated otherwise.

For all cardiovascular endpoints that include time-to-event data the same models and testing procedures as the primary analysis will be applied to compare the two treatment groups.

For continuous secondary diabetes related endpoints with several on-treatment measurements change from baseline will be evaluated with a restricted maximum likelihood (REML) based mixed model repeated measures (MMRM) approach with fixed, categorical effects of treatment, week, treatment-by-week interaction, with the continuous covariates of baseline and baseline-by-week interaction. For those continuous secondary diabetes related endpoints with only one measurement on treatment an analysis of covariance (ANCOVA) model with the factor treatment and the baseline value of the respective variable as covariate will be performed. For qualitative secondary diabetes related endpoints, a Chi-Square test is used to compare the two treatment groups.

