### **6.7.1 Baseline**

With regard to efficacy and safety endpoints, the term "baseline" refers to the last observed/available measurement prior to administration of any randomised study medication.

A missing baseline value at the randomisation (Visit 2) may be replaced by a value at the beginning of the placebo run-in period (Visit 1b).

The following rule applies to baseline laboratory and ECG measurements, if visit and date/time of lab/ECG sample is not in a corresponding sequence (i.e. earlier date/time documented for a later visit):

If such a discrepancy occurs before first study medication intake, then the observations are sorted by date, time and visit and the last observation up to and including the time of the first administration of study drug is selected as baseline value for analyses.

The following considerations apply for laboratory measurements, if the time of the sample is missing on the day of first study medication intake:

- a) For HbA1c, FPG, triglycerides, proinsulin, C-peptide and antibodies: the measurement will not be considered as baseline
- b) For total cholesterol, HDL cholesterol, LDL cholesterol, creatinine, eGFR, urinary albumin, UACR and all safety lab investigations:  
The last measurement on this day will still be considered as baseline measurement.

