### Concomitant medication

All frequency tabulations will be performed on the TS.

In general, any therapy with the start date equal to the date of first trial drug intake is considered as being taken after first trial drug intake.

Overall concomitant medication use (excluding antidiabetic/background therapy) with an incidence of  $\geq 1\%$  in at least one treatment group per WHO-DD preferred name will be summarised by Anatomical-Therapeutic-Chemical classification level 3 (ATC3). Summaries will be presented for concomitant therapies taken during screening and those taken after first drug intake.

Separate summaries of use of acetylsalicylic acid (ASA), antihypertensives, lipid lowering drugs, P-gp or CYP 3A4 inhibitors and anti-coagulants during screening and those taken after first drug intake will be presented.

Antidiabetic therapies including background therapies taken at screening as well as those started after the date of first trial drug intake will be presented, with categorisation into monotherapy/combination therapy and the number of (oral) antidiabetic drugs. Antidiabetic therapies at screening will be linked to the visit 1a HbA1c to reflect the different categories of inclusion criterion 2.

An antidiabetic therapy that is not a background therapy is considered as being taken at screening, if the start date was before the date of IC and the end date was not earlier than 10 weeks prior to IC. As the start and stop date of the protocol-defined background medication of alpha-glucosidase inhibitor and/or metformin is not recorded in the eCRF, it is assumed, that this background medication was already taken at screening.

Summaries on the total daily dose of metformin at the date before first trial drug intake and last date of trial drug intake will be provided, this includes a categorisation into  $\leq 1500\text{mg}$  or  $>1500\text{mg}$ .

The number of patients with a change in background therapy at any time starting from the date of first intake of trial drug will be presented for metformin as well as alpha-glucosidase inhibitor.

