#### *Change from baseline to final visit on-treatment*

For the investigation of continuous diabetes related endpoints at the final visit, the following analysis of covariance (ANCOVA) model will be applied:

Efficacy endpoint as absolute change from baseline = overall mean + treatment + baseline measurement + random error

This model includes effects accounting for the following sources of variation: 'Treatment', and 'baseline'. 'Treatment' is a fixed classification effect and 'baseline' is a linear covariate. The random error is assumed to be normally distributed with mean 0 and variance  $\sigma^2$ .

The adjusted mean with SE for each treatment group, the adjusted mean difference with SE and the corresponding 95% CI will be reported.

Treatment-specific baseline will be investigated.

Descriptive statistics will be presented.

The analysis will be performed on OC and OC-ROC for HbA1c, FPG and ~~on OC-ROC~~ for Total cholesterol, HDL cholesterol, LDL cholesterol, Triglycerides, Creatinine, eGFR, urinary albumin, UACR and weight.

*Change from baseline over time – considering the design of the trial*

Only data up to the planned week that could theoretically be achieved by all patients will be included in this analysis. This time-point depends on the duration of the trial. If e.g. the trial would run for 7 years in total with 2 years for re-cruiting, the last patient randomised could theoretically only reach the visit at week 260. Then for all patients only the data up to planned week 260 will be included in this analysis.

*a) MMRM*

The change from baseline over time will be evaluated with a restricted maximum likelihood (REML) based mixed model repeated measures (MMRM) approach with the fixed, categorical effects of treatment, week, treatment-by-week interaction, with the continuous covariates of baseline and baseline-by-week interaction.

The baseline and the available longitudinal observations at each post baseline visit until last permanent treatment stop will be used for the analysis of these endpoints at each week.

The adjusted least-squares mean with standard error (SE) per treatment group, the mean difference with SE and 95% CI will be reported at all timepoints.

The average treatment difference over time will be provided in addition to the treatment difference per week for continuous endpoints.

An unstructured covariance structure will be used to model the within-patient errors.

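### The exploratory HbA1c and FPG models adjust for baseline but not for prior SU/glinide use, which is stopped at randomisation; the cost is a modest loss of precision

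*Protocol*

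**What the plan says.** - **Withdrawal.** Protocol 3.3.1 states "Prior SU or glinide treatment will be discontinued at Visit 2, whereas if medications such as metformin and alpha-glucosidase inhibitor are being used", these continue. Protocol 4.1.4 adds "SU/glinide should not be taken in the morning of Visit 2".
- **Entry ranges.** Under Protocol 3.3.2, criterion 2, patients on SU or glinide enter with HbA1c 6.5-7.5%; the others enter with 6.5-8.5%.
- **Baseline.** SAP 6.7.1 defines it as "the last observed/available measurement prior to administration of any randomised study medication".
- **Models.** The MMRM in Protocol 7.3.2 has "fixed, categorical effects of treatment, week, treatment-by-week interaction, with the continuous covariates of baseline and baseline-by-week interaction". SAP 7.5.2.2.1 repeats these terms, and its ANCOVA has treatment and baseline only. Neither model has a term for prior antidiabetic therapy.
- **Randomisation.** Protocol 7.5 stratifies by centre only.
- **Availability of the variable.** SAP 7.2 says "Antidiabetic therapies including background therapies taken at screening as well as those started after the date of first trial drug intake will be presented", with the screening therapies linked to the Visit 1a HbA1c by category of criterion 2. SAP Table 6.2: 1, item D1.1, already requires SU/glinide use at baseline to be identified for each patient.
- **Status.** Protocol 7.3.2 and SAP 7.5.2 class these analyses as exploratory, tested two-sided at 0.05.

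**The concern.** Take two patients with a baseline HbA1c of 7.2%, one on metformin alone and one on metformin plus an SU. The models treat them as alike. Yet the second patient's value was reached with a drug that stops that day, whereas the first keeps the whole background regimen. Their later values are likely to differ for a reason unrelated to random assignment. With no term for prior SU/glinide, that difference goes into the residual variance.

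HbA1c change from baseline is a stated objective (Protocol 2.2). Prior use is fixed before randomisation, so adjusting for it would not affect validity. What is at stake is the width of the confidence intervals for HbA1c and FPG.

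**Working it through.** **1. The plan's own figures.** No SD, standard error or power is stated for HbA1c or FPG, so there is nothing to reproduce on this point. The stated power concerns the primary endpoint and is not affected. It does reproduce: with 631 events, margin 1.3, HR 1.0 and one-sided 2.5%, Φ(√(631/4) × ln 1.3 − 1.96) = Φ(1.335) = 90.9%.

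**2. Inputs.** Protocol 3.3 gives about 6000 patients, so n = 3000 per arm. The rest are assumptions:
- p, the share on prior SU/glinide: 0.15 to 0.45.
- dL and dG, the difference in HbA1c change between prior users and non-users in the linagliptin and glimepiride arms: dL 0.2 to 0.8 points, dG 0 to 0.8.
- s, the residual SD: 0.8 to 1.2 points.

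**3. Formulas** (large sample, 1:1 allocation).
- Variance without the factor: [2s² + p(1−p)(dL² + dG²)] / n
- Reduction from adding it: p(1−p)(dL + dG)² / (2n)

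The percentage reduction does not depend on n. The interval widths below do, and they suppose that all patients contribute data.

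**4. Both arms: p = 0.30, dL = dG = 0.5, s = 1.0.**
- p(1−p) = 0.21
- Numerator without the factor: 2 + 0.21 × 0.50 = 2.105
- Reduction: 0.21 × 1.0² / 2 = 0.105
- Variance: 0.105 / 2.105 = 5.0% lower
- Standard error: 1 − √(2.000 / 2.105) = 2.5% lower
- 95% half-width: 1.96 × √(2.105/3000) = 0.0519, falling to 1.96 × √(2.000/3000) = 0.0506

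**5. Linagliptin arm only: dL = 0.5, dG = 0, otherwise the same.**
- Numerator: 2 + 0.21 × 0.25 = 2.0525
- Reduction: 0.21 × 0.25 / 2 = 0.02625
- Variance 1.3% lower, standard error 0.6% lower
- Half-width 0.0513, falling to 0.0509

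**6. Range.**

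| Setting | Variance | Standard error |
|---|---|---|
| s 1.2, p 0.15, dL 0.2, dG 0 (lowest) | −0.1% | −0.04% |
| s 0.8, p 0.45, dL 0.8, dG 0 | −5.5% | −2.8% |
| s 0.8, p 0.45, dL = dG = 0.8 (highest) | −19.8% | −10.5% |

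Simulated ANCOVAs with 6000 patients, 15-40% prior use, an average difference of 0.3-0.9 points and SD 0.7-0.9 gave variance ratios of 0.73 to 0.99, a fall of 1% to 27%. At 28% use and 0.6 points the ratio was 0.88 (SD 0.7) and 0.92 (SD 0.9).

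**7. Does baseline already absorb the effect?** A simulated ANCOVA with baseline in the model still gave standard-error reductions of about 0.7% (0.5 in the linagliptin arm only), 3.6% (0.5 in both arms) and 7.9% (0.8 in both arms, SD 0.8). These agree with the formula within simulation error. The treatment difference was the same with and without the factor.

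**8. Missing at random.** A simulated repeated-measures analysis removed values after rescue at HbA1c above 7.5%. The full-data treatment difference was 0.218-0.221. The estimate was 0.215-0.218 without the factor (about 0.003 low) and 0.220-0.223 with it (about 0.002 high).

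**The case against.** The strongest reply is that this is a modelling preference. The analyses are exploratory, randomisation protects the estimate, and the absolute gain in step 4 is 0.0519 − 0.0506 = 0.0013 HbA1c points of half-width. No conclusion is likely to turn on that. Every input to the size is assumed, and Protocol 3.3.2 allows enrolment of SU/glinide users to be limited, which favours the low end. All of this stands, and it makes the point a minor one.

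A second reply is that the glimepiride arm replaces the withdrawn drug, so prior use matters only under linagliptin and a main effect recovers little. This does not hold as a general argument, because the relevant contrast is within arm. In each arm prior users and non-users receive the same study drug, and only the prior users lose one. If drug effects are roughly additive, the difference has the same sign and a similar size in both arms. Additivity is itself an assumption; step 5 shows the result if it fails completely.

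A third reply is that the narrower entry range lets baseline HbA1c carry part of the information. It carries some, but the ranges overlap throughout 6.5-7.5%, and step 7 shows a gain after baseline adjustment.

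A reader might infer more than the documents support:
- **Bias in the treatment difference.** Randomisation excludes it, and none appeared in the ANCOVA simulation.
- **A strong predictor.** No document gives the size of the association; the design only makes one likely.
- **A rescue of the missing-at-random assumption.** Step 8 shows no meaningful benefit. SAP 6.6 and 7.5.2.2.1 also already include MMRMs that keep values after rescue (OC-ROC, and OC-ALL for HbA1c, FPG and weight).
- **Prior therapy ignored throughout.** SAP Section 6.4 is not in the text available, and SAP 7.5.2.2.1 mentions a model with a subgroup-by-treatment interaction. A subgroup analysis by prior therapy cannot be ruled out, though it would not change the main models.

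**Conclusion.** The point holds as a small, inexpensive improvement. The HbA1c and FPG models omit a variable that is likely to be prognostic by design and is already recorded. The loss is confined to precision in exploratory analyses; the primary and key secondary tests are untouched.

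Under the both-arms case the variance falls by about 5%, roughly the information from 0.05 × 6000 = 300 patients. That figure rests on 30% prior use, a 0.5-point difference in both arms and SD 1.0, none of which comes from the documents. Across the assumptions examined the reduction runs from under 1% to about 20-27%. FPG was not quantified, because no SD is given and its baseline is only approximately an on-drug value.

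**What to change.** In Protocol 7.3.2 and SAP 7.5.2.2.1, for HbA1c and FPG, pre-specify prior SU/glinide at screening (yes/no) as a factor in the ANCOVA, and as a factor with its week interaction in the MMRM.

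No new data are needed; the cost is wording and some extra MMRM coefficients. The factor and its week interaction together add one coefficient per post-baseline visit. For HbA1c, measured every 16 weeks, that is 256/16 = 16 if the model runs to week 256 (the last such visit within the SAP's week-260 example) and 432/16 = 27 if it runs to week 432. FPG adds three more for weeks 4, 8 and 12.

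The text should say that if the model does not converge, the factor-by-week interaction is dropped and the main effect kept. It should also say where that step falls relative to the existing fallback to AR(1) and then compound symmetry.
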